9.0 STATISTICAL CONSIDERATIONS

9.1 Study Design/Study Endpoints

This is a randomized double-blind controlled trial in participants undergoing allogeneic hematopoietic stem cell transplantation (HSCT) to evaluate if high dose intravenous (IV) thiamine can prevent delirium and minimize the deleterious impact of delirium on health-related quality of life (HRQOL), functional status, and other neuropsychiatric outcomes. We will recruit 60 evaluable patients scheduled for allogeneic HSCT at UNC, randomize them to treatment with high

dose IV thiamine (n = 30) versus placebo (n = 30), and systematically evaluate all participants for delirium and related comorbidities.

Analysis Populations: The Safety Population will be defined as all subjects who were enrolled and received at least one dose of study medication. Efficacy Evaluable Population will be defined as all subjects who received at least 80% (17/21) of total possible intervention doses and participated in at least one delirium assessment weekly.

The primary efficacy endpoint is delirium incidence defined as DRS >12. Secondary endpoints include delirium duration and severity, along with FACT-BMT, PROMIS-D, PTSS-14, ECOG-PS, and MOCA.

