3.0 Criteria for Evaluation / Study Endpoints

3.1 Primary Endpoint

Delirium incidence will be defined as: DRS > 12. Delirium rating scales will be performed at baseline (prior to transplant) and then three times weekly from day after transplant to 30 days after transplant or discharge, whichever comes first.

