7.11 Assessment of Efficacy

In order to be considered evaluable for efficacy, patients must:

- receive all 7 days of the treatment; a patient must receive at least 17/21 (80%) thiamine doses
- have delirium assessed at least weekly until one of the following is met:
 1. The participant is found to be delirious (DRS>12)
 2. The participant is at least 30 days post-transplant
 3. The participant is discharged

If a patient is deemed not evaluable, they will be replaced by a new patient. However, if a patient develops delirium during the intervention, they will still

receive the full 7 day course, not be replaced, and included in the efficacy analysis.

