9.2 Sample Size, Accrual and Duration of Accrual

For the primary objective of comparing delirium incidence between groups, a two group chi-squared test with a 0.050 one-sided significance level will have 80% power to detect the difference between a usual care proportion of 0.445 and an intervention proportion of 0.155 (odds ratio of 0.229) when the evaluable sample size in each group is 30. The anticipated rate of delirium in the control group is based on 43 – 73% incidence of delirium during hospitalization for HSCT reported in the literature. As this is the first study to evaluate the efficacy of thiamine as a prevention strategy for delirium, no data is available to generate an estimate of delirium incidence in the intervention group. However, the odds ratio (OR) hypothesized for this study is in line with other successful delirium prevention trials.^{42,43} Even if the delirium incidence in the IV thiamine group is not this low, the results of this study will provide effect sizes and 95% confidence intervals to power a future larger study.

Our sample will include 60 adult participants. UNC tumor registry records demonstrate that between 2015 and 2016 133 patients were admitted for allogeneic stem cell transplant. We estimate that we will enroll at least 50% of eligible patients, based on recruitment rates described in previous delirium intervention studies,⁴⁴ allowing us to recruit our target of 60 evaluable participants in approximately two years and complete our study in the proposed three year grant period.

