9.3 Data Analysis Plans

To compare delirium incidence, severity, and duration between recipients of high dose IV thiamine and placebo during hospitalization for HSCT. The primary outcome measure is delirium incidence, defined as: DRS > 12. Secondary outcomes are differences in delirium duration (in days) and delirium severity, in which higher DRS scores suggest more severe delirium. A two group chi-squared test will be used to compare rates of delirium in the intervention and control group. Maximum severity score will be analyzed using two group t-tests, and time to delirium will be compared between groups using the Kaplan-Meier

method. For those with delirium, two group t-tests will compare the duration of delirium between intervention groups; Kaplan-Meier methods may also be considered for time to delirium resolution.

To determine if thiamine status is predictive of future delirium onset. We will examine the relationship between thiamine levels at the end of the seven day administration of thiamine and the development of delirium at any point during the thirty days post-transplant or the post-transplant hospitalization, whichever comes first. Patients who develop delirium prior to the end of the thiamine treatment will not be included in this analysis. We will examine the sensitivity and specificity of this relationship with ROC curves, and attempt to find a cutoff for thiamine levels that is associated with the development of delirium.

To investigate the effects of high dose IV thiamine on long-term health-related quality of life (HRQOL), functional status, depression, post-traumatic stress symptoms, and cognitive functioning in patients hospitalized for HSCT. Scores on FACT-BMT, PROMIS-D, PTSS-14, ECOG-PS and MOCA will be compared between intervention and control groups. We will summarize scores on the FACT-BMT, PROMIS-D, PTSS-14, ECOG-PS, and MOCA between the intervention and control groups at one, three, and six months post-transplant. Longitudinal modeling will be performed to examine differences/changes over time.

Safety Analyses: We will tabulate AEs and SAEs, by treatment and placebo, within strata. We will include all AEs which occurred at a rate of more than 5% in any treatment.

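### The only efficacy set is chosen after randomisation, and Sections 7.11 and 9.1 define it differently: use one definition and report an all-dosed analysis beside it

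*Combined protocol and SAP*

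**What the plan says.** Section 9.1 defines two analysis populations. One is a Safety Population of enrolled patients with at least one dose. The other is the Efficacy Evaluable Population, "all subjects who received at least 80% (17/21) of total possible intervention doses and participated in at least one delirium assessment weekly". No all-randomised or all-dosed efficacy set appears.

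Section 7.11 sets its own conditions for being evaluable for efficacy. Patients must "receive all 7 days of the treatment; a patient must receive at least 17/21 (80%) thiamine doses" and "have delirium assessed at least weekly until one of the following is met". The three end points listed are DRS > 12, at least 30 days post-transplant, and discharge. Section 7.11 adds: "If a patient is deemed not evaluable, they will be replaced by a new patient". A patient who becomes delirious during the intervention will still "receive the full 7 day course, not be replaced, and included in the efficacy analysis".

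Section 9.3 says "A two group chi-squared test will be used to compare rates of delirium in the intervention and control group" and names no population. Section 9.2 powers that test "when the evaluable sample size in each group is 30". Section 3.1 schedules the DRS "three times weekly from day after transplant to 30 days after transplant or discharge, whichever comes first".

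**The concern.** Patients are randomised (Section 7.3) before the first dose, so both membership conditions are met or failed afterwards. Dosing can stop for adverse events or intercurrent illness (Section 5.6), and the DRS is not done while a patient is intubated or sedated (Section 7.4). A patient whose course worsens can therefore leave the efficacy set and be replaced, and worsening is plausibly linked to delirium. The arms then compared are no longer the arms that were randomised, and no all-dosed result is planned beside them. Section 9.2 intends the effect sizes to power a larger trial, so any distortion would carry forward.

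Separately, two definitions of the set mean that the same data can yield two primary results. A choice between them after unblinding would not be credible.

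**Working it through.** **1. The plan's own figure.** Inputs from Section 9.2: 0.445 against 0.155, 30 evaluable per arm, one-sided 0.05. Power = Φ{[d√n − 1.645√(2p̄(1−p̄))] / √(p₁(1−p₁)+p₂(1−p₂))}, with d = 0.29 and p̄ = 0.30. This is Φ[(1.588 − 1.066)/0.615] = Φ(0.850) = 80.2%. The stated 80% reproduces, for the evaluable set.

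**2. The two definitions side by side.**

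| | Section 7.11 | Section 9.1 |
|---|---|---|
| Doses | all 7 days, then 17/21 | 17/21 |
| Weekly DRS ends at | DRS > 12, day 30 or discharge | not stated; Section 3.1 supplies day 30 or discharge |
| Delirious during the intervention | kept | not mentioned |

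The substantive conflict is the stop at DRS > 12. Take a patient who completes dosing, first scores above 12 in the second week, and is then intubated and unassessable for a week. Under Section 7.11 the patient is evaluable and counts as an event. Under Section 9.1 the patient is excluded.

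The other two rows are ambiguities. Six full days is 18/21 doses (85.7%): in under Section 9.1, unclear under Section 7.11. Whether delirium during the intervention waives the 17/21 rule is not stated.

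**3. Effect of selection when thiamine does nothing.** The documents give no exclusion rates, so these are assumptions. True risk is p = 0.445 in both arms, a share f of an arm is excluded, and a proportion r of the excluded are delirious. The observed rate is (p − f·r)/(1 − f). The rejection rate is by exact enumeration of the one-sided test at 30 per arm, and is 4.6% with no selection. With r = 0.80:

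- Placebo 5%, thiamine 10%: (0.445 − 0.040)/0.95 = 42.6% against (0.445 − 0.080)/0.90 = 40.6%. Rejection rate 6.3%.
- Placebo 10%, thiamine 5%: 40.6% against 42.6%. Rejection rate 3.2%.
- 10% in both arms: 40.6% in each. Rejection rate 4.5%.

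With r = 0.60 the first two become 5.3% and 3.9%. With r = 0.445 (excluded patients at average risk) the rate stays at 4.6% whatever the imbalance.

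**4. Effect of the two definitions, with no arm imbalance.** Let x and y be the delirious counts out of 30 in each arm, and let a share g of the delirious in each arm later miss a week (a and b patients). Section 7.11 tests x/30 against y/30. Section 9.1 tests (x−a)/(30−a) against (y−b)/(30−b), assuming no further replacement. The chance that one set rejects and the other does not:

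| g | 44.5% vs 15.5% | 44.5% in both |
|---|---|---|
| 5% | 3.9% | 1.1% |
| 10% | 6.4% | 1.8% |

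**5. Power of an all-dosed analysis.** Assume replacement to 30 evaluable per arm and that non-evaluable patients in both arms have the control risk. The thiamine risk is then 0.155(1−f) + 0.445f, the control risk stays at 0.445, and n = 30/(1−f), rounded up.

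| f | n per arm | thiamine risk | power |
|---|---|---|---|
| 5% | 32 | 17.0% | 78.2% |
| 10% | 34 | 18.4% | 75.8% |
| 15% | 36 | 19.9% | 73.1% |
| 20% | 38 | 21.3% | 70.0% |

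**The case against.** This is a single-site Phase II study gathering preliminary data. Investigators, biostatistician, research assistants, nurses and patients are blinded (Section 7.3), and the placebo is an equal volume of saline (Section 5.2), so a large imbalance in exclusions is unlikely. With three DRS assessments a week, the weekly rule is lenient. Section 7.11 keeps patients who become delirious during the intervention, and Section 9.1 may simply be a summary that does not carry its detail. After delirium the DRS becomes daily on weekdays as scheduling permits (Sections 3.2.1 and 7.4), so missing a whole week needs prolonged unassessability. Making the all-dosed set primary would also cost power.

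Much of this stands. It lowers the likely size of the bias and makes the higher values of g in step 4 improbable. It also supports leaving the choice of primary set to the sponsor. It does not remove the structural points. Blinding does not stop treatment from affecting who stays well enough to be dosed and assessed. Section 7.11 protects only delirium during the intervention, so a patient who becomes delirious later still has to meet the dose rule. If Section 9.1 is only a summary, it is still the section that defines the analysis population.

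A reader might go further and treat the dosing wording as a second and third contradiction. The documents do not support that. In Section 7.11 the 17/21 clause can be read as defining what receiving all 7 days means. The sentence on patients delirious during the intervention presupposes a full course, so it need not waive the dose rule.

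**Conclusion.** The concern holds and should be fixed. The implied primary set is selected after randomisation, no all-dosed result is planned beside it, and the current text supports two versions of it. That the test uses the evaluable set is an inference from Sections 7.11, 9.1 and 9.2, because Section 9.3 is silent, but it is the only reading that the documents support.

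The size is modest. With no true effect, the assumed imbalances of 5 percentage points with 80% of the excluded delirious move the rejection rate from 4.6% to 6.3% or 3.2%. The two definitions disagree in about 4% to 6% of trials at Section 9.2's rates if 5% to 10% of delirious patients miss a week.

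A reader might infer that the design inflates type I error. The documents do not show this: the rate moves only if exclusion is both unequal between arms and linked to delirium risk, and it can move either way. Nor do they show that the evaluable set cannot serve as primary in a Phase II trial. The 80% power figure is correct for the set that it describes.

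**What to change.** 1. Use one evaluable definition in Sections 7.11 and 9.1, with the weekly requirement ending at DRS > 12, day 30 or discharge. In the same edit, settle how all 7 days relates to 17/21 doses and whether delirium during the intervention waives the dose rule for analysis. Name the population in Section 9.3.
2. Prespecify an analysis of delirium incidence in all randomised patients who received at least one dose, by assigned arm and regardless of doses received, reported beside the evaluable result. Section 5.7 already provides follow-up after treatment stops. State how patients who die or become unassessable without a DRS > 12 are handled, and add bounding analyses that count them all as delirious and then none as delirious.
3. Report exclusions, replacements and randomised but undosed patients by arm and reason. Section 8.5 already gives the monitoring committee the number not completing treatment with reasons, but does not specify this by arm.
4. State in Section 9.2 that the 80% power applies to the evaluable set.

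The cost is a few sentences, a little more analysis, and lower power in the all-dosed set (step 5). Replacement may continue and no extra enrolment is proposed. Making the all-dosed set primary is defensible, but that is the sponsor's choice.

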9.2 Sample Size, Accrual and Duration of Accrual

For the primary objective of comparing delirium incidence between groups, a two group chi-squared test with a 0.050 one-sided significance level will have 80% power to detect the difference between a usual care proportion of 0.445 and an intervention proportion of 0.155 (odds ratio of 0.229) when the evaluable sample size in each group is 30. The anticipated rate of delirium in the control group is based on 43 – 73% incidence of delirium during hospitalization for HSCT reported in the literature. As this is the first study to evaluate the efficacy of thiamine as a prevention strategy for delirium, no data is available to generate an estimate of delirium incidence in the intervention group. However, the odds ratio (OR) hypothesized for this study is in line with other successful delirium prevention trials.^{42,43} Even if the delirium incidence in the IV thiamine group is not this low, the results of this study will provide effect sizes and 95% confidence intervals to power a future larger study.

Our sample will include 60 adult participants. UNC tumor registry records demonstrate that between 2015 and 2016 133 patients were admitted for allogeneic stem cell transplant. We estimate that we will enroll at least 50% of eligible patients, based on recruitment rates described in previous delirium intervention studies,⁴⁴ allowing us to recruit our target of 60 evaluable participants in approximately two years and complete our study in the proposed three year grant period.

9.3 Data Analysis Plans

To compare delirium incidence, severity, and duration between recipients of high dose IV thiamine and placebo during hospitalization for HSCT. The primary outcome measure is delirium incidence, defined as: DRS > 12. Secondary outcomes are differences in delirium duration (in days) and delirium severity, in which higher DRS scores suggest more severe delirium. A two group chi-squared test will be used to compare rates of delirium in the intervention and control group. Maximum severity score will be analyzed using two group t-tests, and time to delirium will be compared between groups using the Kaplan-Meier

method. For those with delirium, two group t-tests will compare the duration of delirium between intervention groups; Kaplan-Meier methods may also be considered for time to delirium resolution.

To determine if thiamine status is predictive of future delirium onset. We will examine the relationship between thiamine levels at the end of the seven day administration of thiamine and the development of delirium at any point during the thirty days post-transplant or the post-transplant hospitalization, whichever comes first. Patients who develop delirium prior to the end of the thiamine treatment will not be included in this analysis. We will examine the sensitivity and specificity of this relationship with ROC curves, and attempt to find a cutoff for thiamine levels that is associated with the development of delirium.

To investigate the effects of high dose IV thiamine on long-term health-related quality of life (HRQOL), functional status, depression, post-traumatic stress symptoms, and cognitive functioning in patients hospitalized for HSCT. Scores on FACT-BMT, PROMIS-D, PTSS-14, ECOG-PS and MOCA will be compared between intervention and control groups. We will summarize scores on the FACT-BMT, PROMIS-D, PTSS-14, ECOG-PS, and MOCA between the intervention and control groups at one, three, and six months post-transplant. Longitudinal modeling will be performed to examine differences/changes over time.

Safety Analyses: We will tabulate AEs and SAEs, by treatment and placebo, within strata. We will include all AEs which occurred at a rate of more than 5% in any treatment.

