7.3 Randomization

If the patient meets all inclusion/exclusion criteria, provides informed consent, and is not delirious ($DRS \leq 12$), the subjects will then be randomized in a 1:1 ratio to the intervention or control arms in a double-blind fashion such that the investigators, biostatistician, CRA(s), nursing staff, and subjects will not know which agent is being administered. The statistician of record will design a block randomization scheme, stratified by age (<65 or ≥ 65) and baseline cognitive function ($MOCA >25$ or ≤ 25), both well-known risk factors for delirium. This information will be provided to UNC Investigational Drug Services, who will manage the actual assignment of subjects to each arm using the randomization list designed by the statistician.

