8.5 Data and Safety Monitoring Plan

This is a Phase II, single site study of 60 individuals to gather preliminary data on the efficacy and safety of high dose IV thiamine for delirium prevention in patients undergoing HSCT. We will follow our standard protocol for monitoring of clinical trials. Subjects are screened to ensure that there are no contraindications to their participation.

The study Co-PIs, Drs. [name] and [name], will be responsible for continuous monitoring of patient safety during the trial. For non-serious Adverse Events (AEs), documentation will begin from the first day of study treatment and continue through the 30 day follow-up period after treatment is discontinued. Collected information will be recorded in Case Report Forms (CRF) for that patient. A description of the event, its

severity or toxicity grade, onset and resolved dates (if applicable), and the relationship to the study drug will be included. For any experience or condition that meets the definition of a serious adverse event (SAE), recording of the event will begin after signing of the informed consent and continue through the 30 day follow-up period after treatment is discontinued. These events will be recorded in the CRF for that patient within 24 hours of learning of its occurrence. If the event is both serious AND unexpected, it will also be recorded on the MedWatch Form 3500A, as per 21 CFR 312.32, and forwarded to the FDA in accordance with 21 CFR 314.80 (for marketed drugs). The UNC IRB will be notified of all SAEs that qualify as an Unanticipated Problem (serious, unexpected, and related) as per the UNC IRB policies. In accordance with these policies, an aggregated list of all SAEs will be submitted to the UNC IRB annually at the time of study renewal.

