10.6 Amendments to the Protocol

Should amendments to the protocol be required, the amendments will be originated and documented by the Principal Investigator at UNC. It should also be noted that when an amendment to the protocol substantially alters the study design or the potential risk to the patient, a revised consent form might be required.

The written amendment, and if required the amended consent form, must be sent to UNC’s IRB for approval prior to implementation.

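### Optional improvement: randomisation is stratified by age and MOCA, but the primary delirium test ignores both factors

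*Combined protocol and SAP*

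**What the plan says.** Section 7.3 specifies 1:1 block randomisation stratified by age (<65 or ≥65) and baseline MOCA (>25 or ≤25), which makes four strata. Its reason is that these are "both well-known risk factors for delirium".

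Section 9.2 sizes the trial on the plain test: "a two group chi-squared test with a 0.050 one-sided significance level will have 80% power" for 0.445 against 0.155 with 30 evaluable patients per arm. Section 9.3 names the same test for the analysis: "A two group chi-squared test will be used to compare rates of delirium in the intervention and control group". No stratified test, adjusted model or covariate is named for delirium incidence. Strata appear in section 9.3 only for safety: "We will tabulate AEs and SAEs, by treatment and placebo, within strata".

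The analysed set is not the randomised set. Section 9.1 defines an efficacy evaluable population, and section 7.11 adds: "If a patient is deemed not evaluable, they will be replaced by a new patient".

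**The concern.** When randomisation is stratified on prognostic factors, the arms are more alike on those factors than chance alone would make them. A test that ignores the strata still uses the full between-patient variance, so its standard error is somewhat too large. The result is a true type I error below nominal and a small loss of power.

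Replacing non-evaluable patients also means that balance within strata is not guaranteed among the patients analysed, which is a further mild reason to stratify the test.

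What is at stake is efficiency, not validity. In a 60-patient trial a point or two of power can be had without recruiting anyone, provided the choice is fixed before unblinding. Made afterwards, it would look data-driven.

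**Working it through.** **1. The plan's own figure.** The inputs are in section 9.2: p₁ = 0.445, p₂ = 0.155, n = 30 per arm, one-sided α = 0.05.

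- Odds ratio: (0.155/0.845) / (0.445/0.555) = 0.2288 (stated 0.229).
- Mean proportion: 0.30. Null standard error: √(2 × 0.30 × 0.70 / 30) = 0.1183.
- Alternative standard error: √[(0.445 × 0.555 + 0.155 × 0.845) / 30] = 0.1122.
- Power: Φ[(0.290 − 1.645 × 0.1183) / 0.1122] = Φ(0.85) = 80.2%.

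Exact binomial enumeration gives 81.1%. A two-sided test would have 69.8%. The stated 80% therefore belongs to the one-sided, uncorrected, unstratified test, and it is right.

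**2. The comparison.** In stratum k let n_k be the number of patients, m_k the number with delirium, n_ck and n_tk the control and thiamine numbers, and x_ck the delirium count on control. The CMH statistic without continuity correction is

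z = Σ(x_ck − n_ck m_k / n_k) / √[Σ n_ck n_tk m_k (n_k − m_k) / (n_k²(n_k − 1))],

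and it rejects if z > 1.645. The sparse-stratum rule uses counts only. If any of the four strata has fewer than 5 evaluable patients, stratify by one factor: the one whose smaller level holds more evaluable patients (tie: MOCA).

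**3. Assumptions, because the documents give none of these.**

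- Shares aged ≥65 / MOCA ≤25 of 30%/50%, 10%/30% or 40%/20%, with the factors independent.
- Blocks of 4 with all patients evaluable, or blocks of 6 with 20% non-evaluable and replaced.
- A treatment odds ratio common to all strata, with marginal rates held at 44.5% against 15.5% for power, or 44.5% in both arms for size.

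**4. Results,** from 40,000 simulated trials per setting:

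| Odds ratio for delirium | Power change with CMH (points) | True size of chi-squared test |
|---|---|---|
| 1 on both factors | -0.7 to 0.0 | 4.5-4.9% |
| 2 on both | +0.1 to +0.7 | 4.3-4.9% |
| 3 on both | +0.9 to +2.1 | 3.8-4.5% |
| 5 on both | +2.2 to +4.2 | 3.1-3.8% |
| 3 on MOCA only | 0.0 to +1.4 | not tabulated |
| 3 on age only | -0.4 to about +1.2 | not tabulated |

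Unstratified power is 80.8-82.8% in every setting. The size of CMH with the rule is 4.5-5.2% throughout, and 4.7-5.0% at an odds ratio of 3. Monte Carlo error is 0.04-0.12 points for the power difference and about 0.11 points for size. Part of the shortfall in size is discreteness: with no prognostic factor and 44.5% in both arms, the exact size of the chi-squared test is 4.6%.

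**5. Sensitivity.** A second simulation used shares of 20%/30% and 30%/40%, blocks of 4, all patients evaluable and CMH on all four strata without the rule. The power change was -0.5 and -0.2 points at odds ratio 1, +0.5 and +0.6 at 2, and +1.9 and +2.3 at 3.

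**6. How often the rule acts.** The smallest expected stratum is 60 × 0.30 × 0.50 = 9 patients at 30%/50%, 60 × 0.10 × 0.30 = 1.8 at 10%/30%, and 60 × 0.40 × 0.20 = 4.8 at 40%/20%. The rule fires in about 8%, 99% and 55-56% of trials respectively. It falls back to MOCA in over 99% of firings at the first two splits, and to age in over 99% at the third.

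**7. Interval estimate.** The mean 95% half-width for the risk difference is 21.6 points unadjusted. Adjustment (Mantel-Haenszel risk difference) narrows it by 0.2-0.4 points at odds ratio 2 and by 0.5-0.9 at 3. Coverage of the adjusted interval is 93.8-94.7%, so no gain is claimed here.

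**The case against.** The strongest reply is that this is a preference. Nothing in the protocol is contradicted. Section 7.3 explains why the factors balance the arms and promises no adjusted analysis. The chi-squared test keeps its stated power, and a true size below 5% protects against false positives. Section 8.5 describes the study as one "to gather preliminary data on the efficacy and safety of high dose IV thiamine". Section 9.2 falls back on effect sizes and intervals for a later trial, which adjustment hardly improves. The benefit rests on assumed figures, and its range includes zero and small losses. The remedy replaces one simple test with one selected by stratum counts, and if few patients are 65 or older the four-stratum test would almost never be run. The change would also come late, since the protocol is already at Amendment 8.

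Most of this stands, and it is why the point is only an option. The conservative size and the lost power are one effect seen twice, not two benefits. A small loss is possible even when one factor is strongly prognostic: up to 0.4 points if only age matters and the rule falls back to MOCA.

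The reply does not remove the asymmetry. If section 7.3 is right that both factors predict delirium, stratifying the test gains power in every setting simulated with an odds ratio of 2 or more on both. If neither matters, the loss is at most 0.7 points.

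**Conclusion.** The mismatch is real and minor. The planned test is valid, agrees between sections 9.2 and 9.3, and delivers its power. A stratified test would be worth less than 1 point of power at an odds ratio of 2 on each factor and about 1-2 points at 3. It would bring the true size from 3.8-4.5% to 4.7-5.0% in the latter case. It would be worth nothing, or cost up to 0.7 points, if neither factor is prognostic. These figures depend on assumed stratum shares, prognostic strength, block size and non-evaluable rate. The direction depends only on how prognostic the factors are. The trial can proceed without the change.

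**What to change.** In section 9.3, make the primary test a one-sided 0.05 CMH test stratified by the two randomisation factors, and keep the chi-squared test as supporting. State the sparse-stratum rule described above, fixed before unblinding and using counts only. A stratum-adjusted risk difference may be reported beside the unadjusted one. The sample size need not change.

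A simpler fallback is always to stratify by MOCA. At the 40%/20% split the count-based choice beats it by 0.1-0.6 points if both factors are prognostic (odds ratios 2-5) and by 0.8-0.9 if only age is (odds ratio 3). It loses 0.4-0.6 if only MOCA is (odds ratio 3). Either is defensible if written down in advance.

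Both factors are recorded before randomisation, so no new data are needed. The cost is a slightly more complex rule and an amendment under section 10.6: "The written amendment, and if required the amended consent form, must be sent to" the IRB for approval before use. It is best bundled with another change.

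The same amendment could add a sentence on how baseline scores enter the model behind "Longitudinal modeling will be performed to examine differences/changes over time". That is missing detail on secondary endpoints and carries no weight in the case above. ECOG-PS (ordinal) and PTSS-14 (some items refer to the transplant unit) would each need their own statement.
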